6.2. Medical History

Patient medical history data including specific details will be presented in a listing for the Safety Analysis Population.

6.3. Inclusion and Exclusion Criteria

Patients who meet all of the protocol defined inclusion criteria and none of the exclusion criteria will be enrolled into the study. Inclusion/exclusion criteria data will be summarized and listed for the Screening Population.

7. Treatments and Medications

7.1. Prior and Concomitant Medications

All medications taken within 28 days prior to the date of study screening will be recorded in the CRF. Concomitant medication will be coded according to the World Health Organization Drug Dictionary (WHODD, version 01SEP2015). A prior medication is defined as any medication that has a stop date before the date of first dose of study drug. A concomitant medication is defined as any medication that has a stop date on or after the date of first dose of study drug.

The number and percentage of patients who used prior or concomitant medications will be summarized in two separate tables by Anatomical Therapeutic Chemical (ATC) level 4 and preferred term, maximum dose levels and overall using the Safety Analysis Population.

All prior and concomitant medication will be presented in a listing for the Screening Population.

Imputation for missing medication start dates and stop dates can be found in Appendix 15.4.

Medications with missing stop dates after imputation will be classified as both prior and concomitant.

7.2. Study Treatments

A 400 mg *bid* initial oral dose of PRN1008 will be used in this study, and dosage will be adjusted during the treatment of study drug. Patients will be treated with PRN1008 for a maximum of 12 weeks. Tablets may be taken with or without food.

7.2.1. Extent of Exposure

Overall duration of exposure is defined as the total number of days a patient is exposed to the study drug and will be presented as the total number of days from the first dose date (Day 1) to the last dose date:

$$\text{Overall Duration of Exposure} = \text{Date of last dose} - \text{Date of first dose} + 1.$$

If date of last dose date is missing, date of last visit during the treatment will be used.

The average daily dose will also be introduced to characterize features of the dose adjustment design adopted in this study, which is calculated as the following:

$$\text{Average Daily Dose} = \text{Cumulative dose} / \text{Overall duration of exposure}$$

The cumulative dose will be defined as the sum of doses taken by patients during the treatment.

The overall duration of exposure and average daily dose will be summarized using descriptive statistics overall and by maximum dose level in a table for all patients in the Safety Analysis Population.

The number of adjustments in dose level and the minimum dose level will also be summarized.

Patient's overall duration of exposure, average daily dose, minimum dose level, maximum dose level, and number of adjustments in dose will be presented in a listing for the Safety Population.

7.2.2. Treatment Compliance and Modifications

Study drug accountability will be performed during the treatment. Patients will be asked to bring back all remaining study drug and all study drug packaging at each study visit for drug accountability.

The overall study drug compliance (%) will be calculated as following:

$$\text{Overall Compliance (\%)} = \frac{\text{Total number of tablets taken during the treatment}}{\text{Total number of tablets planned during the treatment}} * 100$$

The total number of tablets taken will be calculated by subtracting the number of tablets returned from the number of tablets dispensed. The total number of tablets planned will be calculated by multiplying the total number of days of planned exposure to study drug by the number of tablets planned per day.

The overall study drug compliance will be summarized by descriptive statistics overall and by maximum dose level. The number and percentage of patients in compliance category of <80%, >=80 and <=120%, and >120% will also be presented.

Study drug dispensed and returned and study drug compliance will be presented in two listings by patient for the Safety Analysis Population.

8. Efficacy Analysis

All efficacy analyses will be conducted using the ITT, mITT and PP Analysis Population.

All efficacy analyses consider CS used in endpoints to be systemic CS only, i.e. oral (not mouthwash), intramuscular or intravenously administered. Topical CS are not considered systemic CS.

For cumulative by visit summaries, unscheduled visits are not included in the summary. For other by visit summaries, unscheduled visits, if exists in the data, will be presented separately after other visits. All visits will be presented in listings.

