8.1. Primary Efficacy Endpoint

The primary efficacy endpoint is “The proportion of patients who are able to achieve CDA within 4 weeks of starting PRN1008 treatment without the need for doses of prednis(ol)one >0.5 mg/kg at any time”.

Other types of CS are converted to dose-equivalent prednis(ol)one (see Section 8.2.6).

This is operationalized as meaning the first CDA is achieved on or before the Week 5 visit but after first dose of PRN1008, and will be summarized, by maximum dose level to the Week 5 visit and overall in a table, using frequencies and percentages. In addition, two-sided 80% and 95% CIs (Confidence Intervals) of the response rate will be provided for each maximum dose level and overall using the Exact (Clopper-Pearson) method.

Patients who are able to achieve CDA between first dose of study drug and the Week 5 visit and have no occurrence of daily prednis(ol)one >0.5 mg/kg before the date of the first CDA will be considered as responders, even if the CDA status was not maintained or higher doses of prednis(ol)one were used after the first CDA. Patients who are not able to achieve CDA prior to or at the Week 5 visit or have any occurrence of daily prednis(ol)one >0.5 mg/kg before a first CDA during the study treatment will be considered as non-responders. Patients whose CDA status is unknown at the Week 5 visit for whatever reason (include early termination before Week 5 visit) will be also considered as non-responders. Only systemic CSs (as defined by medication taken orally or intravenously) are to be used to evaluate the efficacy endpoints, topical CSs will not be counted.

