8.2.7. Cumulative CS Usage

Cumulative corticosteroid (CS) usage per patient (mg) over 12 weeks will be presented overall and by maximum dose level in a table. Only subjects who complete at least 12 weeks of treatment (terminated at or after the Week 13 (Day 85) Visit) will be included. To calculate this endpoint, the following steps will be followed:

- Step 1: All other CSs will be converted into prednisolone/prednisone dosage equivalent. Each 10 mg of prednisolone is equivalent to 10 mg of prednisone, 8 mg of methylprednisolone, 1.5 mg dexamethasone, 40 mg hydrocortisone or 1.5 mg betamethasone.
- Step 2: The CSs usage will be converted to standard frequency using the following conversion chart, the standard frequency is in the first column (i.e., mg/day).

Standard frequency	Unit	Frequency	Conversion factor
mg/day	mg	QD	1
mg/day	mg	BID	2
mg/day	mg	QOD	0.5
mg/day	mg/day	Any value	1
mg/day	mg	ONCE	1
mg/day	mg	Q24H	1
mg/day	mg	TID	3
mg/day	mg	QS	0.1428571
mg/day	mg	QID	4

Once the CSs type and frequency are converted as above, each record of CSs taken will be converted to prednisolone with standard frequency (mg/day).

- Step 3: The duration for each record of CSs (CS) taken will be calculated using the formula: Duration = CS end date – CS start date + 1, in days. Any missing start or end date of CSs taken will be imputed using the algorithm specified in Section 15.4.
 - If the CS end date is after the date of Week 13 (Day 85) - 1, then the CS end date will be replaced by the date of Week 13 (Day 85) - 1; if the CS end date is before the study treatment start date, this record will not be used to summarize cumulative dose for CSs.
 - If the CS start date is before the study treatment start date, then the CS start date will be replaced by the study treatment start date (i.e. Day 1); if the CS start date is after the date of Week 13 (Day 85) - 1, this record will not be used to summarize cumulative dose for CSs.

- Note that above date adjustments only apply to cumulative CS dose calculation. Other analyses, where CS dose is needed, will use CS start and end dates as reported.
- Step 4: The “record” level cumulative CSs usage will be calculated as: record level cumulative dose = standard frequency * duration (days).
- Step 5: The patient level cumulative CSs usage will be calculated as the summation of all the non-missing record level cumulative doses.

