5.4.1 Primary Efficacy Endpoint

The primary efficacy endpoint is:

- The proportion of patients who are able to achieve CDA within 4 weeks (on or prior to Week 5 visit) of starting PRN1008 treatment **without** the need for doses of prednis(ol)one > 0.5 mg/kg

The Control of Disease Activity (CDA) responses are assessed at visits specified in the Schedule of assessments (Table 1). Types of CS other than prednis(ol)one are converted to dose-equivalent prednis(ol)one (see Section 5.4.2.3).

This is operationalized as meaning the first CDA is achieved on or before the Week 5 visit but after first dose of PRN1008, and will be summarized, by dose level to the Week 5 visit and overall in a table, using frequencies and percentages. In addition, two-sided 80% and 95% CIs (Confidence Intervals) of the response rate will be provided for each dose level and overall.

Patients who are able to achieve CDA between first dose of study drug and the Week 5 visit without prednis(ol)one >0.5 mg/kg on the date prior to the CDA will be considered as responders, even if the CDA status was not maintained or higher doses of prednis(ol)one were used after the first CDA. Patients who are not able to achieve CDA prior to or at the Week 5 visit or had prednis(ol)one >0.5 mg/kg on the date prior to CDA will be considered as non-responders. Patients whose CDA status is unknown at the Week 5 visit for whatever reason (including early termination before Week 5 visit) will be also considered as non-responders. Only systemic CSs (as defined by medication taken orally or intravenously) are to be used to evaluate the efficacy endpoints, topical CSs (including buccal CS) will not be counted.

The number and percentage of patients who meet the primary efficacy endpoint criteria will be tabulated by dose level and overall (all patients).

A sensitivity analysis using the Completer and PP population will be provided.

Panel plots will be provided for PDAI score over the study period for each patient. Dose level (mg/day) will also be plotted on the same figure. Lines for the steroid equivalent dose in mg/kg will be added to the plots. A total of 9 plots (3 x 3) will be fitted on one page.

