5.4.2.3 Cumulative Corticosteroid (CS) Usage

Cumulative corticosteroid (CS) usage per patient (mg) will be presented by treatment period (up to first 12 weeks, after first 12 weeks, entire treatment period and follow-up period), by dose level and overall in a table. To calculate this endpoint, the following steps will be followed:

Step 1: Select CSs with route = “ORAL” or “INTRAVENOUS”. The CSs will be converted into prednisolone/prednisone dosage equivalent using the below conversion chart.

CS medication	Conversion factor
Prednisone, Prednisolone	1
Hydrocortisone	0.25
Methylprednisolone, Methylprednisolone Sodium Succinate	1.25

Dexamethasone, Betamethasone	6.67
------------------------------	------

Step 2: The CSs usage will be converted to standard frequency using the following conversion chart.

Frequency	Unit	Conversion factor
QD, Q24H, ONCE, CONTINUOUS, BD PRN, PRN	mg	1
5 TIME A DAY	mg	5
QID	mg	4
TID	mg	3
2-3 DAILY	mg	2.5
BID	mg	2
QOD, EVERY 2 DAYS	mg	1/2
BIS	mg	2/7
QS, EVERY WEEK	mg	1/7
Any value	mg/day	1

Once the prednisolone/prednisone dosage equivalent and frequency are converted as above, each record of CSs taken will be converted to prednisolone with standard frequency (mg/day).

Step 3: The duration for each record of CS taken will be calculated using the formula: Duration = CS end date – CS start date + 1, in days. Any partial start or end date of CSs taken will be imputed using the algorithm specified in Section 3.5.1. If the CS start date is completely missing, then the date will be imputed as Week 1 Day 1, i.e. it is assumed that the medication is taken at the study entry. If the CS stop date is completely missing, then the date will be imputed as Date of End of Study, i.e. it is assumed that the medication is taken up to the end of study.

If the CS start date is before the Week 1 Day, then the CS start date will be replaced by the Week 1 Day 1; if the CS start date is after the date of Week 29 (Day 197) - 1, this record will not be used to summarize cumulative dose for CSs.

If the CS end date is after the date of Week 29 (Day 197) - 1, then the CS end date will be replaced by the date of Week 29 (Day 197) - 1; if the CS end date is before the study treatment start date, this record will not be used to summarize cumulative dose for CSs.

Note that above date adjustments only apply to cumulative CS dose calculation. Other analyses, where CS dose is needed, will use CS start and end dates as reported.

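### Intramuscular corticosteroid counts as systemic in Part A SAP section 8, but the Part A responder rules and the Part B SAP leave it out

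*SAP*

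**What the plan says.** The Part A SAP opens section 8 (Efficacy Analysis) with a general rule for all efficacy analyses, under which the CS that counts is systemic only, meaning "oral (not mouthwash), intramuscular or intravenously administered". Topical CS is excluded.

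Section 8.1, the primary endpoint, gives a narrower rule: "Only systemic CSs (as defined by medication taken orally or intravenously) are to be used to evaluate the efficacy endpoints". Sections 8.2.1 (control of disease activity, CDA, without CS), 8.2.2 (complete response, CR, without CS) and 8.2.3 (CR without prednis(ol)one above 0.5 mg/kg) repeat that rule. Section 8.2.7 (cumulative use) applies no route filter: "All other CSs will be converted into prednisolone/prednisone dosage equivalent".

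The Part B SAP uses only the narrower rule. Section 5.4.1 reads "Only systemic CSs (as defined by medication taken orally or intravenously) are to be used" and excludes topical and buccal CS. Section 5.4.2.3 opens with "Step 1: Select CSs with route" equal to ORAL or INTRAVENOUS, and its Step 5 sets the cumulative dose to 0 when no record qualifies. The primary endpoint (5.4.1) and the CS dose on the day before each visit (5.4.2.4) both take their conversion from 5.4.2.3.

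Neither list of changes to the planned analysis (Part A SAP 13, Part B SAP 4.7) mentions the counted routes.

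**The concern.** The primary endpoint and the steroid-free endpoints depend on detecting systemic CS. Part A itself classes the intramuscular route as systemic, yet the sections that decide who is a responder omit it. Two programmers working from the same Part A SAP could therefore classify the same patient differently. Under the narrower rule, a Part A patient could be a steroid-free responder and still show a non-zero cumulative dose under 8.2.7.

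In Part B, a patient whose only systemic CS was intramuscular would receive a cumulative dose of 0 and could be counted as achieving CDA on zero steroids. The protocol allows Parts A and B to be combined (11.9.1), so a pooled rate could mix two definitions of steroid use. The study has no control arm and is meant to inform confirmatory trials (protocol 11.4), which makes a consistent responder definition worth having.

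**Working it through.** **Routes, place by place**

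| Place | Routes counted | Intramuscular |
|---|---|---|
| Part A 8, general rule | oral except mouthwash, intramuscular, intravenous | counted |
| Part A 8.1, 8.2.1, 8.2.2, 8.2.3 | oral, intravenous | not counted |
| Part A 8.2.4, 8.2.5, 8.2.7, 8.2.8 | no route limit of their own, so section 8 governs | counted |
| Part B 5.4.1 | oral, intravenous | not counted |
| Part B 5.4.2.3 Step 1 | ORAL, INTRAVENOUS | not counted |
| Part B 5.4.2.4 | converted through 5.4.2.3 | not counted |

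**Direction of the error**

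- Endpoints without CS or without more than 0.5 mg/kg (Part A 8.1 to 8.2.3; Part B 5.4.2.1 items 2, 4, 7, 10, 13, 15 and the primary endpoint): ignoring a dose can turn a non-responder into a responder, never the reverse.
- Part B cumulative and per-visit CS dose: ignoring a dose can only lower the figure.
- Endpoints with more than 0.5 mg/kg (Part B 5.4.2.1 items 3, 6, 9, 12, 14): ignoring a dose lowers the count.
- CDA with no steroid condition (Part B items 1 and 5): route plays no part.

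**The plan's own figure.** Both SAPs give an 80% CI of ±13% at a 50% response rate with 25 patients. The normal approximation gives 1.2816 × √(0.5 × 0.5 / 25) = 1.2816 × 0.1 = 0.128, or 12.8 points. The figure reproduces and is not in dispute.

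**Size of one reclassified patient.** 1/25 = 4.0 points. Exact (Clopper-Pearson) 80% intervals, assuming for illustration that 13 responders are counted:

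| Responders | Rate | 80% CI |
|---|---|---|
| 13/25 | 52.0% | 37.5 to 66.2 |
| 12/25 | 48.0% | 33.8 to 62.5 |
| 11/25 | 44.0% | 30.1 to 58.7 |

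The second and third rows show one and two patients removed. Part B efficacy uses the mITT population (5.4). If that is smaller than 25, one patient is worth 100/n points.

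**When a dose disqualifies under the 0.5 mg/kg rule.** Take the Part B conversion factors and divide the threshold by the factor:

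- methylprednisolone: 0.5 / 1.25 = 0.4 mg/kg
- dexamethasone or betamethasone: 0.5 / 6.67 = 0.075 mg/kg
- hydrocortisone: 0.5 / 0.25 = 2.0 mg/kg

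Without other CS, a dose at or below these values does not change the primary endpoint. For the endpoints that require no CS at all, any dose in the window disqualifies.

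**How long a single injection counts.** In both SAPs a record with frequency ONCE has factor 1, and duration is end date minus start date plus 1. An injection with the same start and end date therefore counts for one day.

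- Part A 8.1 looks for any day above 0.5 mg/kg before the first CDA, so that one day would be seen once the route is admitted.
- Part B 5.4.1 looks only at the date before CDA. If CDA is dated Day 15, an injection is seen on Day 14 but not on Days 1 to 13. Adding the route alone would usually not catch it.

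**The case against.** The strongest reply is that the conflict may never touch a patient. Where the rescue appendices give a CS route it is oral, and protocol 6.3.2 names oral, inhaled and mucosal CS. No document reports an intramuscular dose. Both SAPs also list all CS use with its route, so an intramuscular record would be visible. All of this stands, and it is why the severity is minor. It does not remove the conflict, because section 8 expressly provides for this route.

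A second reply is that Part B is a separate SAP and agrees with itself. That is also correct: Part B contains no internal contradiction. It leaves out a route that the same study's Part A SAP calls systemic, and gives no reason.

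A reader might infer more than the documents support:

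- That the narrower rule always flatters the drug. It does not: the endpoints with more than 0.5 mg/kg move the other way.
- That 4 points is the expected bias. It is a ceiling for one patient, with conditions attached.
- That Part A cumulative use (8.2.7) also needs repair. It has no route filter, and section 8 governs it.

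**Conclusion.** The plan is wrong as written, with minor severity. Part A states two incompatible definitions of systemic CS for its responder endpoints, and Part B applies the narrower one throughout.

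The size is at most 4 points on an overall rate per affected patient at n = 25. Reaching it requires that the patient otherwise be a responder, that the intramuscular dose be large enough to disqualify, and that it fall in the counted window (before first CDA for the Part A primary endpoint, the date before CDA for Part B). The number of such patients is unknown and may be zero. The documents therefore do not support saying that any response rate is inflated.

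**What to change.** 1. Use the section 8 definition (oral excluding mouthwash, intramuscular, intravenous) in Part A SAP 8.1, 8.2.1, 8.2.2 and 8.2.3, in Part B SAP 5.4.1, and in the route filter at Part B 5.4.2.3 Step 1. Leave Part A 8.2.7 as it is.
2. Add one sentence to the analysis rules of each SAP stating how many days a single injection counts toward the daily prednisolone-equivalent. Without it, the first change has little effect on the Part B primary endpoint.
3. Record both changes in the lists of changes to the planned analysis.

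The cost is a few words in six places, one new analysis rule per SAP and a small programming change. Route is already collected and listed, so no new data are needed. If the listings contain no intramuscular record, no result changes. If they do, the affected responder and CS-dose tables are rerun.

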8.1. Primary Efficacy Endpoint

The primary efficacy endpoint is “The proportion of patients who are able to achieve CDA within 4 weeks of starting PRN1008 treatment without the need for doses of prednis(ol)one >0.5 mg/kg at any time”.

Other types of CS are converted to dose-equivalent prednis(ol)one (see Section 8.2.6).

This is operationalized as meaning the first CDA is achieved on or before the Week 5 visit but after first dose of PRN1008, and will be summarized, by maximum dose level to the Week 5 visit and overall in a table, using frequencies and percentages. In addition, two-sided 80% and 95% CIs (Confidence Intervals) of the response rate will be provided for each maximum dose level and overall using the Exact (Clopper-Pearson) method.

Patients who are able to achieve CDA between first dose of study drug and the Week 5 visit and have no occurrence of daily prednis(ol)one >0.5 mg/kg before the date of the first CDA will be considered as responders, even if the CDA status was not maintained or higher doses of prednis(ol)one were used after the first CDA. Patients who are not able to achieve CDA prior to or at the Week 5 visit or have any occurrence of daily prednis(ol)one >0.5 mg/kg before a first CDA during the study treatment will be considered as non-responders. Patients whose CDA status is unknown at the Week 5 visit for whatever reason (include early termination before Week 5 visit) will be also considered as non-responders. Only systemic CSs (as defined by medication taken orally or intravenously) are to be used to evaluate the efficacy endpoints, topical CSs will not be counted.

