8.2.2. Achieved CR without CS within 12 Weeks

The proportion of patients who are able to achieve CR without CSs within 12 weeks will be summarized in the same way as that described in Section 8.1. Patients who are able to achieve CR between treatment start date and the Week 13 visit and have no occurrence of any CS after the treatment start date and before the first CR visit during the study treatment will be considered as responders. Patients who are not able to achieve CR between start of treatment and the Week 13 visit or have any occurrence of any CS between start of treatment and a first CR visit during the study treatment will be considered as non-responders. Patients whose CR status is unknown at the Week 13 visit for whatever reason (include early termination before Week 13 visit) will be also considered as non-responders. Only systemic CSs (as defined by medication taken orally or intravenously) are to be used to evaluate the efficacy endpoints, topical CSs will not be counted.

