8.2.3. Achieved CR without Prednis(ol)one >0.5 mg/kg within 12 Weeks

The proportion of patients who are able to achieve CR without the need for doses of prednis(ol)one of greater than 0.5 mg/kg within 12 weeks will be summarized in the same way as that described in Section 8.1. Patients who are able to achieve CR at any visit on or before the Week 13 visit during the study treatment and have no occurrence of daily prednis(ol)one >0.5 mg/kg between the first dose date of PRN1008 treatment and the day before the date of the first CR will be considered as responders. Patients who are not able to achieve CR at all visits on or before the Week 13 visit during the study treatment or have any occurrence of daily prednis(ol)one >0.5 mg/ between the first dose date of PRN1008 treatment and the day before the date of the first CR will be considered as non-responders. Patients whose CR status is unknown at all visits on or before Week 13 visit during the study treatment for whatever reason (include early termination before Week 13 visit) will be also considered as non-responders. Only systemic CSs (as defined by medication taken orally or intravenously) are to be used to evaluate the efficacy endpoints, topical CSs will not be counted.

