 Patients who achieved CDA at or prior to the Week 5 visit and had no occurrence of daily prednis(ol)one >0.5 mg/kg before the first CDA date during the study treatment will be counted as responders.
 Two-sided 80% and 95% confidence intervals are calculated using the Exact (Clopper-Pearson) method.
 Percentages are based on the number of patients in the respective dose levels in the Analysis Population.

Source Data: Listing 16.2.4.1.1

<DIRECTORY PATH>PROGRAM NAME Executed: DDMMYYYY hh:mm

Prog note: Early treatment terminators or subjects whose CDA status are completely missing are considered non-responders.

Repeat this table for the other populations:

Table 14.2.1.2
 Proportion of Patients who Achieved Control of Disease Activity (CDA) at or Prior to Week 5 Visit without
 Prednis(ol)one >0.5 mg/kg
 mITT Population

Table 14.2.1.3
 Proportion of Patients who Achieved Control of Disease Activity (CDA) at or Prior to Week 5 Visit without
 Prednis(ol)one >0.5 mg/kg
 Per Protocol Population

Table 14.2.2.1.1
 Proportion of Patients who Achieved Control of Disease Activity (CDA) at or Prior to Week 5 Visit without Corticosteroids
 ITT Population

	400 mg (N=xx)	500 mg (N=xx)	600 mg (N=xx)	Total (N=xx)
n (%)	xx (xx.x)	xx (xx.x)	xx (xx.x)	xx (xx.x)
80% CONFIDENCE INTERVAL	(xx.x, xx.x)	(xx.x, xx.x)	(xx.x, xx.x)	(xx.x, xx.x)
95% CONFIDENCE INTERVAL	(xx.x, xx.x)	(xx.x, xx.x)	(xx.x, xx.x)	(xx.x, xx.x)

Note: Patients are classified into different dose levels according to the maximum dose they received during the 12 week treatment period.
 Control of disease activity (CDA) is defined as the time at which new lesions cease to form and established lesions begin to heal.
 Patients who achieved CDA at or before the Week 5 visit and had no occurrence of any corticosteroid before the first CDA visit during the study treatment will be counted as responders.
 Two-sided 80% and 95% confidence intervals are calculated using the Exact (Clopper-Pearson) method.
 Percentages are based on the number of patients in the respective dose levels in the Analysis Population.

Source Data: Listing 16.2.4.1.2

<DIRECTORY PATH>PROGRAM NAME Executed: DMMMMYYYY hh:mm

Prog note: Early treatment terminators or subjects whose CDA status are completely missing are considered non-responders.

Repeat this table for the other populations

Table 14.2.2.1.2
 Proportion of Patients who Achieved Control of Disease Activity (CDA) at or Prior to Week 5 Visit without Corticosteroids
 mITT Population

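### Part A SAP 8.1 makes a patient with CDA before Week 5 but no Week 5 status both a responder and a non-responder, mainly in the ITT tables

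*SAP*

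**What the plan says.** **Responder rule.** Part A SAP 8.1 operationalises the endpoint as meaning that "the first CDA is achieved on or before the Week 5 visit but after first dose of PRN1008". Patients who meet this without prior prednis(ol)one above 0.5 mg/kg "will be considered as responders, even if the CDA status was not maintained or higher doses of prednis(ol)one were used after the first CDA".

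**Unknown-status rule.** The same paragraph also has this rule: "CDA status is unknown at the Week 5 visit for whatever reason (include early termination before Week 5 visit) will be also considered as non-responders". It makes no exception for a CDA already documented.

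**Table 14.2.1.1 shell.** The footnote gives the responders as "Patients who achieved CDA at or prior to the Week 5 visit and had no occurrence of daily prednis(ol)one >0.5 mg/kg"; its steroid condition ends at the first CDA. The programming note below it reads: "Early treatment terminators or subjects whose CDA status are completely missing are considered non-responders".

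**Source listings.** Listing 16.2.4.1.1, the named source of that table, flags a responder only when CDA is achieved at the Week 5 visit itself. Listing 16.2.4.1.2 (steroid-free CDA, Week 5) and Listing 16.2.4.1.3 (steroid-free complete response, Week 13) follow the same pattern.

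**Related endpoints.** Section 8.2.1 repeats the 8.1 wording for steroid-free CDA. For complete response (CR), 8.2.2 makes non-responders of "Patients whose CR status is unknown at the Week 13 visit for whatever reason", whereas 8.2.3 does so only for "Patients whose CR status is unknown at all visits on or before Week 13 visit". Section 8.2.5 carries an earlier response forward to visits the patient no longer attends.

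**Part B.** SAP 5.4.1 has the same pair of rules, the second beginning "Patients whose CDA status is unknown at the Week 5 visit for whatever reason (including early termination before Week 5 visit".

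**The concern.** Week 3 (Day 15) is a scheduled response visit, so CDA can be on record two weeks before the cut-off. If such a patient then has no Week 5 status, 8.1 classifies the patient twice, in opposite directions. The primary ITT rate then depends on which sentence the programmer follows. Table 14.2.1.1 and the Week 5 row of Table 14.2.2.4.5.1 could also report different counts for what should be the same quantity.

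A tie-break is worth fixing in advance here. The study is open-label, and SAP section 11 cites an interim report of August 2018 on 26 patients with at least 4 weeks of therapy. The shells became final on 20 December 2018.

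**Working it through.** **1. The plan's own precision figure.** Part A SAP 4.1 gives n = 25, a 50% response rate and an 80% CI of ±13%. The Wald half-width is 1.2816 × √(0.5 × 0.5 / 25) = 0.128, or 12.8 points, which rounds to 13. The exact (Clopper-Pearson) method that 8.1 specifies for the analysis gives a half-width of 14.4 points at 12/25 or 13/25.

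**2. Classifying four patients under each rule.** All have a qualifying CDA with no prior prednis(ol)one above 0.5 mg/kg. R = responder, NR = non-responder, – = the rule is silent.

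| Patient | 8.1 responder rule and table footnote | 8.1 unknown-status rule | Programming note, read literally | Listing 16.2.4.1.1 | 8.2.5 at Week 5 |
|---|---|---|---|---|---|
| CDA Day 15, leaves before Week 5 | R | NR | NR | NR | R |
| CDA Day 15, on drug, Week 5 visit missed | R | NR | – | NR | R |
| CDA Day 15, stops drug, attends Week 5 | R | – | NR | R only if CDA is present at Week 5 | R |
| CDA at Week 5, stops drug at Week 9 | R | – | NR | R | R |

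The first two rows are the contradiction inside 8.1; it needs an absent Week 5 status. The last two arise only from the note. The listing differs even with complete data: a CDA reached at Day 15 and lost by Week 5 is R under 8.1 and NR in the listing. The listing's steroid condition also runs to the Week 5 visit, not to the first CDA.

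**3. The CR endpoints.** Take a steroid-free CR at Week 9 with no Week 13 status. Section 8.2.3 gives R. Section 8.2.2 gives both R and NR. Listing 16.2.4.1.3 gives NR.

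**4. Which analysis sets are exposed.**
- Part A ITT (4.3.3): every dosed patient, so fully exposed.
- Part A mITT (4.3.4) needs Week 5 follow-up and PP (4.3.5) needs the Week 13 visit, so both largely exclude the patient caught by 8.1. mITT does not require Week 13, so the 8.2.2 overlap can occur there too.
- Part B (5.4) uses mITT for efficacy, with Completer and PP as sensitivity sets. Under 3.2.4 to 3.2.6 these require a Week 5 disease assessment, a Week 29 assessment and the Week 29 visit respectively.

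**5. Size.** One patient in 25 is 1/25 = 4 points. Assume 13 of 25 ITT patients meet the responder rule and k of them have no Week 5 status. The exact limits are the α/2 quantile of Beta(x, n − x + 1) and the 1 − α/2 quantile of Beta(x + 1, n − x).

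| k | Responder rule prevails | Unknown-status rule prevails | 80% CI | 95% CI |
|---|---|---|---|---|
| 0 | 13/25 = 52% | 13/25 = 52% | 37.5 to 66.2 | 31.3 to 72.2 |
| 1 | 52% | 12/25 = 48% | 33.8 to 62.5 | 27.8 to 68.7 |
| 2 | 52% | 11/25 = 44% | 30.1 to 58.7 | 24.4 to 65.1 |
| 3 | 52% | 10/25 = 40% | 26.5 to 54.8 | 21.1 to 61.3 |

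The intervals belong to the unknown-status column. Three patients move the rate 12 points, close to the planned half-width of 12.8.

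**The case against.** **The affected group is narrow.** The patient must respond early and then have no Week 5 status. This is a pilot sized pragmatically for a point estimate; p-values are only informative and no success threshold depends on the rate. That stands, and it limits the severity.

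**Unknown as non-response is a defensible conservative rule.** That also stands. The fault is the missing precedence, not the choice, so whichever rule is not chosen belongs in a sensitivity analysis.

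**The programming note may be shorthand.** A reader might infer that it turns every early treatment terminator into a non-responder, including someone who responds by Week 5 and stops at Day 60. The documents do not support that as a settled rule. Section 8.1 limits early termination to the time before Week 5, and the footnote of the same table counts that patient as a responder. The note can also be read with missing status governing both groups, though it would then differ from 8.1's Week 5 condition. Nor does its reference to completely missing status make an early terminator a responder: the note only lists non-responders. What remains is an ambiguous note with no time limit.

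**Part B is not at risk.** A reader might infer that its primary result is equally ambiguous because the wording is repeated. Its efficacy populations make the unknown-status sentence practically redundant.

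**Conclusion.** The contradiction in Part A SAP 8.1 is real and recurs in 8.2.1 and 8.2.2. It bears mainly on the Part A ITT tables, and in Part B it is essentially a matter of tidiness. The programming note is ambiguous, and Listings 16.2.4.1.1 to 16.2.4.1.3 use a different rule.

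The size is 4 points per affected patient at the planned 25. The number affected is not in the documents: 0 to 3 patients (0 to 12 points) and the 13/25 starting count are assumptions, so the table shows sensitivity and does not estimate bias. Nor do the documents show that the rule was left open with results in mind; the interim date only shows why it should be settled. This should be fixed, but it does not undermine the design.

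**What to change.** - **Sections 8.1, 8.2.1 and 8.2.2:** follow the 8.2.3 pattern. A qualifying response documented on or before the cut-off visit counts as response. The unknown-status and early-termination rule applies only to patients with no qualifying response by then.
- **Programming notes under the CDA and CR tables:** limit them to termination before the cut-off visit without a prior qualifying response.
- **Listings 16.2.4.1.1 to 16.2.4.1.3:** align the responder flag and its steroid condition with the section text.
- **Part B SAP 5.4.1:** make the same edit for consistency.
- **Reporting:** give the number of responders with no cut-off assessment, and add a sensitivity analysis counting them as non-responders.

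The cost is SAP and shell wording plus one extra table. No new data are needed.
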